### 3.4.2.5 Overall Survival

Overall survival (OS) is defined as the time from randomization until death due to any cause. A subject alive at the end of study or lost to follow-up will be censored for OS at the last date when the subject was known to be alive. The last date for each individual subject is defined as the latest among the following dates recorded on the case report forms (CRFs):

- AE start, stop, and change dates
- Admission and discharge dates of hospitalization
- Start date of protocol deviations
- Study treatment date
- Date of last contact, withdrawal consent, refuse to be followed up, or last known alive on end of treatment, end of study, and survival status/follow-up CRFs
- Laboratory test dates including (but not limited to) hematology, chemistry, urinalysis, coagulation, tumor biopsy, immunoglobin, pharmacokinetics, pharmacodynamic biomarkers.
- Disease assessment dates on RECIST CRF
- Date of visit, vital signs, ECOG, electrocardiogram, and physical examination
- Start and stop dates of alternative anticancer treatment
- Start and end date of concomitant medication and surgical/medical procedure

OS is defined in months as follows:

$$\text{OS (months)} = (\text{Date of death or censoring} - \text{Date of randomization} + 1) / (365.25/12).$$

The number and percentage of subjects experiencing an OS event and Kaplan-Meier plots of OS will be presented by treatment group. The median OS and its 95% CI will be estimated using the Kaplan-Meier method. The proportion of subjects alive at 12 months (OS-12) and

associated 95% CI will be estimated using the Kaplan-Meier method. Additional OS landmarks to be included in the final analysis are OS-18, OS-24, and OS-36.

The difference in OS between groups will be tested for significance by using a stratified log-rank test on histology (adenocarcinoma vs non-adenocarcinoma). The log-rank test will be carried out with the Breslow method for handling ties. The hazard ratios of each experimental arm vs. control arm with two-sided 95% CI will be estimated by a stratified Cox regression model on histology with ties handled by the Efron method ([Efron et al, 1977](#)).

The comparison of OS-X (X=12, 18, 24, 36 months) between the 2 treatment arms will be performed by normal approximation under cloglog transformation ([Klein et al, 2007](#)), where the event is death. The test statistic is defined in Section [3.4.2.4](#).

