#### **4.1.5 Withdrawal from the Study**

Subjects are free to withdraw their consent to participate in the study (study treatment and assessments) at any time, without prejudice to further treatment. All study drug(s) should be

returned by the subject. If a subject withdraws from further participation in the study, then no further study visits or data collection should take place.

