#### 4.2.3 End of Study

**Table 7** presents procedures for the end of study visit for all subjects. End of study visit will be performed when a subject discontinues study due to a confirmed PD, or a subject experienced an unconfirmed PD but is not eligible for a confirmation scan, or after 60 months of follow-up for subjects who achieve DC and remain disease free, or at the last study visit for subjects who discontinue study due to reason not related to PD.

Subjects who discontinue treatment due to any reason, including confirmed PD or initiation of alternative anticancer therapy, will be followed for survival according to the timepoints in **Table 6** (every 8 weeks up to 12 months post Cycle 1 Day 1, every 12 weeks from > 12 to ≤ 24 months, and every 6 months from > 24 to 60 months post Cycle 1 Day 1) unless the subject withdraws consent from further participation in the study. After 60 months, subjects may be contacted for survival every 12 months until the end of the entire study.

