5.0	04SEP2023	
 
1. Added a few terms in the list of abbreviations
 
2. Section 3.1 clarified for the definition of baseline
 
3. Updated SAS version to 9.4
 
4. Table 3.2-1 Added PK-evaluable population
 
5. Section 3.3.3 removed data cut-off from duration of exposure definition
 
6. Section 3.3.4 add ATC and WHO Drug version
 
7. Section 3.3.5 Added COVID-19 related IPDs
 
8. Section 3.4.2.4 Added PFS-36 month landmark
 
9. Section 3.4.2.4 Updated and clarified the Greenwood's formula, and added more details
 
10. Section 3.4.2.5 Added OS-36 month landmark
 
11. Section 3.5 Updated section to clarify that no pharmacodynamic analyses are planned at this stage
 
12. Section 3.6 Added clarification regarding any derivation timeframe (in Labs, VS, ECOG)
 
13. Section 3.6.4 Updated wording to increase readiness and match what the expectations are, for the laboratory tables
 
14. Section 3.6.4 Creatinine clearance rate formula added
 
15. Section 3.6.5.1 Removed 10% subjects wording and added minimum and maximum post-baseline summaries of vital signs
 
16. Section 3.6.5.2 Added information as to why no ECG analyses are planned for the CSR
 
17. Section 3.6.5.4 Added a section for physical examinations (none planned)
 
18. Section 3.8 Added PK analysis plan
 
19. Section 3.8 Mentioned that all results to be reported in ug/mL
 
 
Other minor clarifications were made throughout.
	
 
1. Previously missing some abbreviations, and new ones corresponding to new updates
 
2. Lack of information in defining baseline when no time indicator captured
 
3. Latest SAS version available
 
4. SAP now includes PK analysis
 
5. No DCO defined in final CSR
 
6. Clarify that the summary of concomitant medications is by ATC and PT
 
7. COVID-19 related IPDs might be required for the CSR
 
8. Agreed with the team in prior communications to include PFS-18, PFS-24 and PFS-36 landmarks for the CSR
 
9. Lack of precision in the formula details (<math>n_i</math> refers to deaths or disease progressions in the PFS section, difference between <math>i</math> and <math>k</math>)
 
10. Agreed with the team in prior communications to include OS-18, OS-24, and OS-36 landmarks for the CSR
 
11. Previous version outdated (MedImmune process) - Wording confirmed with PK/PD team
 
12. Discussed during the Dry Run review with the team to consider only post-baseline visits up to and including 90 days post last dose of study drug
 
13. Wording was unclear and disorganized, clarification was needed
 
14. Information more complete with additional details provided
 
15. CSP doesn't mention a selection criterion (10% of subjects) so not needed here, but mentions min/max summaries of vital signs
 
16. CSP mentions ECG analyses while ECGs were only collected at screening
 
17. CSP mentions physical examination statistical analysis,
 

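### With no OS cutoff and no close-out survival contact, OS-36 and the tail of the OS curve can be biased downward if follow-up at the final analysis is short

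*SAP*

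**What the plan says.** Under SAP 3.4.2.5, anyone still living when the study closes, or no longer traceable, "will be censored for OS at the last date when the subject was known to be alive". That date is the latest of a long list of case report form dates. One entry reads "Date of last contact, withdrawal consent, refuse to be followed up, or last known alive on end of treatment, end of study", and the entry goes on to the survival follow-up form. The rule names no cutoff date. The same section says: "Additional OS landmarks to be included in the final analysis are OS-18, OS-24, and OS-36". It compares these landmarks between arms and also reports the median.

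The only statement about a cutoff for the final report is in the SAP version history (version 5.0): "No DCO defined in final CSR". It is given there as the reason for a change to the definition of exposure duration, not as an OS rule. By contrast, Protocol 4.8.3 ties PFS censoring to a data cutoff.

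Protocol 4.2.3 schedules survival contacts every 8 weeks in the first year, then "every 12 weeks from > 12 to ≤ 24 months", then "every 6 months from > 24 to 60 months post Cycle 1 Day 1". After month 60, contact is optional and yearly. Protocol 5.4.3 requires all deaths in the study and its follow-up to be reported. Protocol 6.3 ends the study 5 years after the last subject enters, or earlier if the sponsor stops it. Neither document describes a contact of all living subjects at the time of the final analysis.

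**The concern.** The rule can treat deaths and survivors unequally near the end of follow-up. Take two subjects randomized 34 months before the analysis and last contacted at month 30. One dies at month 33 and the site reports it, so an event is counted at month 33. The other is alive but has not been contacted again, so censoring is at month 30 and that subject is not in the risk set at month 33. The death is divided by too few subjects at risk, and the Kaplan-Meier estimate falls too far.

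The effect builds up in the last contact interval before the analysis date. After month 24 that interval is long, and OS-36 lies in this range. At stake are the level of OS-36, the shape of the tail and whether a median is reported as reached. These figures would be used to judge later development and to compare with other studies.

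**Working it through.** **1. Contact gap from the plan's own figures.** SAP 3.4.2.4 gives the length of two missed assessments as 126, 182 and 422 days. These follow from the Protocol Table 6 intervals plus the windows the SAP adds:
- to month 12: 2 × (56 + 7) = 126 days
- months 12 to 24: 2 × (84 + 7) = 182 days
- after month 24: 2 × (183 + 28) = 422 days

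All three reproduce. Survival contacts use the same intervals. A single gap after month 24 is therefore 183 days nominally and 211 days with the window: 211 / 30.4375 = 6.9 months. In months 12 to 24 it is at most 91 days, or 3.0 months.

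**2. When OS-36 can be affected.** A living subject must have a last contact before month 36. If contacts fall exactly on month 36, this needs less than 36 months since randomization. If they do not, it needs less than 36 + 6.9 = 42.9, about 43 months.

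**3. Size.** The documents give no OS rates, accrual period or minimum follow-up, so these are assumptions:
- exponential survival, with 24-month survival of 65% or 75%, or OS-36 of 50%, 65% or 75%
- uniform accrual over 12 or 18 months
- contacts on the protocol schedule

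The runs used 200,000 or 400,000 simulated subjects per setting. Deaths counted up to the analysis date, and living subjects were censored at their last contact. For example, with 65% alive at 24 months the true OS-36 is 0.65^(36/24) = 0.524. With 12-month accrual and 30 months' minimum follow-up, Kaplan-Meier gave 0.471, which is 5.3 points low.

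| Minimum follow-up | OS-36 too low by (points), all deaths reported at once |
|---|---|
| 24 months (18-month accrual) | 3.5 to 7 |
| 30 months | 1 to 5 |
| 33 months | 1 to 2 |
| 36 months | 0 to 1 |
| 43 months or more | 0 |

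The spread within a row comes from the survival rate, the accrual period and where contacts fall relative to month 36. If half the deaths are reported at once, the bias is about half. If deaths are learned only at scheduled contacts, it is zero. With a common cutoff and everyone's status confirmed at it, it is zero within simulation error (about 0.15 points).

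OS-12 and OS-18 do not move. OS-24 moves by 0.4 to 0.6 points, and only at 24 months' minimum follow-up.

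For scale, the standard error of OS-36 with 60 subjects is √(S(1 − S)/60): 6.5 points at S = 50%, 6.2 at 65% and 5.6 at 75%.

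**4. Median.** With 75% alive at 24 months the true median is 24 × ln 0.5 / ln 0.75 = 57.8 months. The table shows how often a median is reached with 60 subjects and 12-month accrual.

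| Minimum follow-up | Deaths reported at once | SAP rule | Cutoff and contact round |
|---|---|---|---|
| 36 months | all | 49% | 20% |
| 36 months | half | 33% | 18% |
| 43 months | all | 60% | 37% |
| 43 months | half | 47% | 37% |

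With 65% alive at 24 months the effect is smaller: 91% against 81% at 36 months, all deaths reported at once.

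**5. Difference between arms.** With an assumed hazard ratio of 0.7 and all deaths reported at once, the OS-36 difference shifts by 0.6 to 0.9 points at 24 to 30 months' minimum follow-up, and by at most 0.4 from 33 months (simulation noise about 0.2).

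**The case against.** The strongest reply is that the bias needs two conditions that the documents do not establish.

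- **Short follow-up.** The planned end of study is 5 years after the last subject. An analysis then has no OS-36 bias, and the absence of a cutoff fits an analysis at study end. This stands for OS-36, but the sponsor may stop earlier. SAP version 4.0 (February 2023) was already written for the final report, four years after version 1.0 (February 2019). An analysis before the 5-year mark is plausible, though this is inference because accrual and analysis dates are not stated.
- **Deaths learned between contacts.** Protocol 5.4.3 sets a 24-hour clock only for deaths not clearly due to progression. Progression deaths go into the case report form with no stated timing, and many may surface at scheduled contacts. This stands and would shrink the bias. No rule holds deaths back to the next contact, however.

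The list of last-alive dates includes laboratory, hospital and treatment dates, so real gaps may be shorter than simulated. That helps subjects still attending visits more than those followed for survival only.

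A reader might infer three stronger things that the documents do not support:
- **That the late landmarks are certainly biased.** They may not be, for the two reasons above, and among landmarks only OS-36 moves materially.
- **That the comparison between arms is distorted.** Both arms share one contact schedule and only concurrent controls are used. The shift is under about 1 point.
- **That stopping data at withdrawal adds a further bias.** Protocol 4.1.5 does say of withdrawn subjects "then no further study visits or data collection should take place". Nothing in the documents allows an effect to be sized or shows that it would differ by arm, and subjects who only stop treatment are still followed for survival. It is not part of this point.

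**Conclusion.** The point holds as a conditional one. The OS rule has no cutoff and no close-out contact, so it permits deaths to count beyond the time at which living subjects leave the risk set. Whether this biases the result depends on how deaths are learned and on follow-up at the analysis. In the least favorable settings OS-36 is low by about one standard error of a 60-subject arm. With 36 months' minimum follow-up it is low by at most about 1 point. The tail and the median are more exposed: they can still be affected at 43 months, when OS-36 is already clean.

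All sizes rest on assumed exponential survival and uniform accrual. OS is a secondary endpoint in a study with no power or Type I error target, and the primary response analysis is untouched. The change is worth making because it is cheap and removes the problem.

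**What to change.** In SAP 3.4.2.5:
- Set one OS cutoff date for the final analysis.
- Confirm the vital status of every subject still in follow-up on or just after that date.
- Censor subjects confirmed alive at the cutoff.
- Do not count deaths after the cutoff.
- Report minimum follow-up beside OS-36.

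The cost is one survival contact round, which Protocol Table 6 already allows by telephone once visits have stopped, and a few late deaths that are not counted.

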### **3.3    Study Subjects**

#### **3.3.1    Subject Disposition and Completion Status**

Subject disposition and completion status will be summarized for all subjects screened, and percentages will be based on subjects randomized and treated. In addition, disposition of subjects throughout the study with respect to discontinuation of treatment and end of study status including reasons will be provided. Summaries of the number and percentage of subjects entered at each site will be provided.

The mortality summary will include subjects with end of study status of death, as well as cause of death (toxicity related to IP or disease under investigation, or other).

Duration of follow-up will also be summarized.

A listing of global/country study disruptions (impacting visits, concomitant medications and/or exposure) will be provided.

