### **3.3.3 Study Drug Exposure**

- Treatment exposure will be summarized for the As-treated population. Duration of exposure to IP(s) in weeks and cycles will be summarized by descriptive statistics and by frequency. The duration of exposure for each IP is defined as below. last dose date plus the dosing interval (days) minus first dose date for subjects who completed treatment.
- minimum of (date of death plus 1 day, last dose date plus the dosing interval) minus first dose date for subjects who discontinued treatment.

Dose intensity and relative dose intensity of IP(s) will be summarized by descriptive statistics. The relative dose intensity is a percent of total actual dose that a subject received during corresponding study treatment period versus the total intended dose for the same study treatment period according to the study protocol. The details of the dose intensity calculation will be provided in the SPP as part of the standard exposure TFL templates.

Dosing deviations for IP(s), per the CRF, will be summarized with reasons for deviations for the following categories: delays, omissions, and interruptions. Duration of dosing delays will be derived where a delay is flagged on the CRF, based on the scheduled dosing dates and the visit window. The number of subjects with dosing delays and total dose delays will be summarized.

The use of subsequent anticancer treatment after the discontinuation of study treatment will be summarized by the type of subsequent anticancer treatment if data allow.

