### **3.3.5 Protocol Deviations**

The incidence of important protocol deviations will be summarized by deviation categories. The COVID-19 related IPDs will also be summarized. A listing will be provided with protocol deviation details. None of the deviations will lead to subjects being excluded from any analysis populations described in Section 3.2, unless otherwise specified. If a deviation is serious enough to have a potential impact on the primary analysis, sensitivity analyses may be performed.

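### The OS last-known-alive date accepts any protocol-deviation start date, which does not necessarily show that the subject was alive

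*SAP*

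**What the plan says.** SAP section 3.4.2.5 states the principle first: a subject who is alive or lost to follow-up is "censored for OS at the last date when the subject was known to be alive". It then turns the principle into a derivation, taking the latest of a list of CRF dates. Most items record something done with or to the subject: dosing, laboratory samples, scans, visits, vital signs, last contact and survival status. One does not have to: "Start date of protocol deviations". It carries no qualifier, and nothing elsewhere in the SAP or protocol limits it to deviations recorded at a contact.

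The SAP also expects disruption during the study. Section 3.3.5 says of important protocol deviations (IPDs): "The COVID-19 related IPDs will also be summarized". Section 3.3.1 says: "A listing of global/country study disruptions (impacting visits, concomitant medications and/or exposure) will be provided".

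**The concern.** Because the rule takes the latest date, one late entry is enough to set the censoring date. If a deviation is recorded because a subject did not attend, its start date can fall on a day when nobody knew whether the subject was alive. The subject then stays in the OS risk set, without an event, beyond the last real evidence of life, and the Kaplan-Meier estimate moves up.

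The SAP treats missed assessments the opposite way for PFS. Under its censoring table (Table 3.4.1), progression or death directly after two or more missed or non-evaluable assessments is censored back to the last progression-free assessment before the gap. For OS, a record that a visit was missed could carry censoring forward.

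What is at stake is a set of secondary results: the OS curves and medians, the landmark rates at 12, 18, 24 and 36 months, and the tests built on them.

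**Working it through.** The documents state no OS event count, power or loss rate that depends on this rule, so there is no plan figure to reproduce. The check has four steps.

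**1. When the item changes anything.** It sets the censoring date only if (a) no death is recorded and (b) the deviation start date is later than every other date on the list. A deviation at an attended visit, dose, blood draw, scan or call should already be matched by another listed date. The item therefore acts mainly when no contact is recorded on or after the deviation date.

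**2. Shift per affected subject.** Inputs: the survival follow-up intervals in protocol section 4.2.3 and Table 6, and the SAP's month of 365.25/12 = 30.4375 days. Assumption: a missed-visit deviation is dated to the next scheduled contact.

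| Period | Interval | One missed contact | Two in a row |
|---|---|---|---|
| To month 12 | 8 weeks = 56 days | 56/30.4375 = 1.84 months | 3.68 |
| Months 12-24 | 12 weeks = 84 days | 84/30.4375 = 2.76 months | 5.52 |
| Months 24-60 | 6 months | 6.0 months | 12.0 |

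The year-1 figure is for a subject in follow-up. During treatment, visits are every 28 days (protocol Table 5), so one missed visit would add 28/30.4375 = 0.92 months.

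**3. How many subjects.** The documents give no loss rate. At an assumed 5-10%, 0.05 × 60 = 3 and 0.10 × 60 = 6 subjects per arm are lost. This is an upper bound on those affected, because each must also meet conditions (a) and (b).

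**4. Effect on OS at 36 months (OS-36).** Illustrative simulation with 60 subjects in an arm and 1,500 runs per setting. All inputs are assumed: exponential survival with true OS-36 of 50-70%; 5-20% lost, uniformly over months 0-36 and independently of death; administrative censoring uniform over months 36-60. Every lost subject is given a deviation one or two scheduled intervals after last contact, capped at administrative censoring. Mean rise in the Kaplan-Meier OS-36 estimate, in percentage points:

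| True OS-36 | 5% lost, one / two intervals | 10% lost, one / two | 20% lost, one / two |
|---|---|---|---|
| 50% | 0.15 / 0.29 | 0.32 / 0.57 | 0.69 / 1.22 |
| 60% | 0.13 / 0.24 | 0.28 / 0.50 | 0.61 / 1.05 |
| 70% | 0.11 / 0.19 | 0.22 / 0.40 | 0.48 / 0.87 |

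At 5-10% lost, the range of means is 0.11-0.57 points. The largest single run was 3.03 points at 5-10% lost and 4.21 points at 20%. Person-time rose by 0.38-1.59% at 5-10% lost.

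For scale, at an assumed OS-36 of 60% and ignoring censoring before month 36, the 95% confidence half-width for one arm is 1.96 × √(0.6 × 0.4/60) = 12.4 points. The matching mean shifts of 0.13-0.50 points are 0.13/12.4 = 1% to 0.50/12.4 = 4% of it.

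The simulation covers one arm at a time. It gives no estimate of an effect on the hazard ratio or the log-rank test.

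**The case against.** The strongest reply is that the mechanism depends on a convention the documents do not contain. Neither document says how a missed visit is dated, or that a lost subject's missed visit or call is logged as a deviation at all. That stands, and it is why the shifts in step 2 are conditional.

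Texts that seem to supply the mechanism give it little support. SAP section 3.3.3 summarizes dosing deviations "for the following categories: delays, omissions, and interruptions". These belong to the exposure summary, are not shown to be the protocol deviations meant in 3.4.2.5, and can arise only during treatment of up to 12 months. The COVID-19 provisions show that disruption was expected, but not how it would be dated.

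The affected group is also narrowed by design. All subjects are followed for survival unless they withdraw consent (protocol section 4.1.6), and Table 6 allows telephone contact once visits stop. Survival-form dates are already on the list, so a later successful contact makes the deviation date irrelevant. Some deviations, such as a procedural error at an attended visit, do coincide with contact.

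These points bear on frequency and size. They leave the gap in the rule: as written, a date without evidence of life can set OS censoring.

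A reader might also infer that the item tilts the comparison between arms, since the trial is open-label and losses or missed visits could differ by arm. The documents give no loss or deviation rates by arm, so that is not supported.

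**Conclusion.** The point holds as a minor defect of definition. A deviation start date does not necessarily show that the subject was alive, so the list can conflict with the principle it is meant to implement. It would go too far to say that the list contradicts the principle outright, or that 3-6 subjects per arm will be wrongly censored. The first ignores deviations recorded at a contact; the second turns an upper bound into an estimate.

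On the stated assumptions about dating and loss, the mean effect on OS-36 is about 0.1-0.6 percentage points, upward within an arm and small beside the sampling error. It would be larger only if loss were common: 0.48-1.22 points at 20%. Any effect on the hazard ratio depends on losses or deviations differing by arm. OS is a secondary endpoint, and the primary objective response analysis does not use this date.

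**What to change.** Delete the protocol-deviation item from the list in SAP section 3.4.2.5. Alternatively, keep it but accept a deviation date only when the record documents contact with the subject on that date. Deletion should lose almost no valid information, because the other listed dates should already cover attended visits, doses, samples, scans and calls.

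As a check, report by arm the number of subjects whose OS censoring date was set by a deviation date alone. If it is zero, the item had no effect.

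The cost is one line of SAP text and one input to the derivation. Deletion needs no new data; the alternative needs a look at the deviation records concerned.
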